### **Treatment Period Visits**

Patients on episodic or prophylactic treatment in this study participate in regular interim visits for follow up, as well as follow up at specific ED milestones. Regular interim visits were every 12 ( $\pm 2$ ) weeks.

### **ED Milestone Visits**

Unscheduled visits are performed at the following ED milestones to perform protocol-mandated inhibitor tests: 5 EDs ( $\pm 2$  EDs), 10 EDs (10-15 EDs), 20 EDs (20-25 EDs) and 50 EDs (50-55 EDs).

### **Surgery Visits**

Surgery visits are as follows:

- Pre-Surgery Visit (Week -4 to Week -2). Not required for emergent surgery.
- Preoperative Assessment (Day of Surgery). If surgery is delayed by  $\geq 8$  weeks, preoperative assessments are to be repeated. These include assessments of FIX activity and Nijmegen-modified Bethesda assay. For minor surgery, the Investigator will be in contact with the patient or patient’s parent/caregiver to determine when the patient should return to the regular pre-surgery regimen.
- Postoperative Visit (1 to 2 weeks after surgery). Visit is required for major surgeries only.
- Last Postoperative Visit. This visit occurs when the Investigator determines that the patient can return to the regular pre-surgery regimen and is not required if the return to the regular pre-surgery regimen occurs at the Postoperative Visit. If the subject is withdrawn from the study, then he will complete ET/EOS Visit assessments at least 2 weeks after surgery.

	Statistical Analysis Plan	Final v1.0
---	----------------------------------	-------------------

## ITI Visits

After a patient on episodic or prophylactic treatment is confirmed as having high-titer inhibitors, or low-titer inhibitors with poorly controlled bleeding, the patient may participate in ITI visits. Pre-ITI assessment is on ITI Week 0. Interim ITI visits are every 4 weeks ( $\pm 2$  weeks) from ITI Week 4 to Week 24, and subsequently every 12 weeks ( $\pm 2$  weeks) from ITI Week 36 until End of Treatment (EOT).

## End-of-Treatment Visit

End of Treatment (EOT) for individual patients is defined as follows:

- A patient who completes at least 50 EDs of rFIXFc and is not on an ITI regimen, is considered to have completed treatment.
- A patient undergoing ITI with rFIXFc is considered to have completed treatment if either of the following occurs:
  - The patient achieves successful immune tolerance as defined in protocol [Section 10.2.6](#).
  - The patient completes 24 months on an ITI regimen without achieving successful immune tolerance.
- Individual patients may also have to end treatment because one of the following has occurred:
  - The patient meets the criteria for early withdrawal.
  - Study stopping rules are met.
  - EOS is reached.

Upon ending treatment for any of the reasons described above, the subject will return to the site for the ET/EOS visit.

## Final Safety Follow-Up Visit

The Final Safety Follow-Up Visit (by telephone or in person) will be conducted within 14 (+7) days after the last dose of rFIXFc to assess the patient's status, collect AEs and/or SAEs, collect concomitant medications and procedures, and follow up on open AEs and SAEs.

### 5.2.4. Study-Specific Definitions

#### Exposure Day

One ED is defined as a 24-hour period in which a patient receives 1 or more doses of rFIXFc, with the time of the first injection of rFIXFc defined as the start of the ED.

#### Bleeding Episode

A bleeding episode is defined as follows: A bleeding episode starts from the first sign of a bleed, and ends no more than 72 hours after the last injection to treat the bleed, within which any symptoms of bleeding at the same location, injections  $\leq 72$  hours apart, are considered the same

	Statistical Analysis Plan	Final v1.0
---	----------------------------------	-------------------

bleeding episode. Any injection to treat the bleeding episode, taken >72 hours after the preceding one, will be considered the first injection to treat a new bleeding episode in the same location. Any bleeding at a different location is considered a separate bleeding episode, regardless of the time from the last injection.

**Spontaneous Bleeding Episode**

Bleeding episodes are classified as spontaneous if a parent/caregiver/patient records a bleeding event when there is no known contributing factor such as a definite trauma or antecedent “strenuous” activity. The determination of “strenuous” is at the discretion of the Investigator, and the parent/caregiver/patient will be instructed on this by the Investigator.

**Traumatic Bleeding Episode**

Bleeding episodes are classified as traumatic if the parent/caregiver/patient records a bleeding episode when there is a known or believed reason for the bleed. For example, if a patient exercises strenuously and then has a bleeding episode in the absence of any obvious injury, the bleeding episode will still be recorded as traumatic. Target joint bleeding episodes can be traumatic if a known action leads to bleeding into the joint.

**High and Low Titer Positive Inhibitors**

A positive inhibitor test result is defined as an inhibitor test result of  $\geq 0.60$  BU/mL that is confirmed by a second test result of  $\geq 0.60$  BU/mL from a separate sample, drawn 2 to 4 weeks following the original sample. Both tests must be performed by the central laboratory using the Nijmegen-modified Bethesda assay. The date of the inhibitor is the date of the sample with the first positive test result which was subsequently confirmed.

- A positive low titer inhibitor is defined as an inhibitor test and confirmatory test, both with results of  $\geq 0.60$  and  $< 5.00$  BU/mL.
- A positive high titer inhibitor is defined as an inhibitor test and confirmatory test, both with results of  $\geq 5.00$  BU/mL.

Patients with discordant inhibitor test results (initial low titer result followed by high titer result or initial high titer result followed by low titer result) should have repeat inhibitor testing performed by the central laboratory from a third separate sample, drawn 2 to 4 weeks following the previous sample.

- If 2 of 3 test results are  $< 5.00$  BU/mL, the inhibitor is considered low titer.
- If 2 of 3 test results are  $\geq 5.00$  BU/mL, the inhibitor is considered high titer.

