7.3.3. Post-Treatment Follow-Up

Subjects will perform the assessments of the Early Termination (ET)/End of Study (EOS) Visit after at least 50 EDs to rFIXFc has been achieved, if they have withdrawn from the study, or the end of study is declared. A Final Safety Follow-up Visit/Telephone Call will be conducted 14 (+7) days after the last dose of rFIXFc to assess the subject's status for AEs, SAEs, and concomitant treatments and procedures. It will be at the discretion of the Investigator to conduct the Final Safety Follow-up Visit by telephone or in person.

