10.2.4. Inhibitor Testing

Subjects will be tested for inhibitor and anti-rFIXFc antibody formation at each clinic visit. Samples for anti-rFIXFc antibody testing (see [Section 10.2.5](#)) will be collected at the same timepoint when any samples are collected for inhibitor testing, including confirmatory and

CONFIDENTIAL

The information contained herein may not be used, disclosed, or published without the written consent of Bioerativ
Therapeutics Inc

unscheduled inhibitor tests, tests for suspected inhibitor development, and as required before and after surgery. Washout prior to sample collection for inhibitor testing should be at least 72 hours. Testing for inhibitors must also be conducted at ED Milestone Visits, as described in Section 4.2.2.2. If these do not align with a scheduled study visit, an additional visit must be scheduled to complete this testing. Additional unscheduled testing for inhibitors may be performed if required by local standards of care, and inhibitor test results must be recorded on the eCRF.

Testing for inhibitors must also be performed 2 to 4 weeks prior to elective major surgery, preoperatively, postoperatively, and at the Last Postoperative Visit (see Section 4.2.3). For minor surgeries, testing for inhibitors will only be performed if indicated by the nature of the procedure, according to local standard of care.

A valid inhibitor test result is required from the ET/EOS Visit. An unscheduled visit may be required to repeat inhibitor testing under this protocol if the ET/EOS Visit inhibitor test is not evaluable, or to obtain samples to confirm a positive inhibitor test result.

In addition, if inhibitor development is suspected at any time during the study (e.g., the expected plasma FIX activity levels are not attained or if bleeding is not controlled with an expected dose), the subject will be tested for inhibitors by the central laboratory.

A positive inhibitor test result is defined as an inhibitor test result of ≥ 0.60 BU/mL that is confirmed by a second test result of ≥ 0.60 BU/mL from a separate sample, drawn 2 to 4 weeks following the original sample. Both tests must be performed by the central laboratory using the Nijmegen-modified Bethesda assay.

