11. WITHDRAWAL OF SUBJECTS FROM THE STUDY

A subject must permanently discontinue study treatment and be withdrawn from the study if any of the following occur:

- The subject is found to have FIX activity >2% or a positive inhibitor based on central laboratory results from samples collected during the screening period
- Development of a Grade 2 or greater allergic drug reaction in association with the administration of rFIXFc, as defined below by the Recommendations for Grading of Acute and Subacute Toxic Effects on the World Health Organization (WHO) scale [[WHO Handbook 1979](#)]:
 - Grade 2: bronchospasm; no parenteral therapy needed
 - Grade 3: bronchospasm; parenteral therapy required
 - Grade 4: anaphylaxis
- Development of a positive inhibitor as defined in Section 10.2.4, either a low titer inhibitor with bleeding that is no longer reliably controlled with rFIXFc or a high titer inhibitor, and opting not to undergo or continue ITI
- Use of FIX products other than rFIXFc (exception allowed for 1 emergency or accidental use); a further exception is the use of activated prothrombin complex concentrate for subjects developing inhibitors (see Section 10.2.6.6)
- Development of any condition that precludes subjects from complying with the study procedures
- A medical emergency that necessitates discontinuation of treatment
- Judgment of the Investigator: a subject may have treatment permanently discontinued if, in the opinion of the Investigator, it is not in the subject's best interest to continue with the study treatment
- The parent/legal guardian can withdraw the subject from the study, or the subject can withdraw from the study, at will at any time
- At the discretion of the Investigator or Sponsor for noncompliance

The reason for the subject's withdrawal from the study must be recorded in the subject's eCRF.

For any subject who is not responding to treatment with rFIXFc, as determined by the Investigator, a decision will be made with the Sponsor whether to continue the subject in the study.

CONFIDENTIAL

The information contained herein may not be used, disclosed, or published without the written consent of Bioerativ
Therapeutics Inc

If the decision is made to withdraw the subject from the study, the ET/EOS Visit assessments will be performed as described in Section [4.2](#).

CONFIDENTIAL

The information contained herein may not be used, disclosed, or published without the written consent of Bioverativ
Therapeutics Inc

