Allergic reactions, including anaphylaxis, have been reported with FIX products. Hypersensitivity reactions have been reported with rFIXFc. These events often occur in close temporal relation with the development of FIX inhibitors. Subjects (as appropriate) and parents/legal guardians of subjects should be informed of early symptoms and signs of hypersensitivity reactions, including difficulty breathing, chest tightness, swelling of the face, rash, or hives. If such an event occurs while the subject is at home, the parents/legal guardians should be instructed to seek immediate medical care for the subject. The presence of inhibitors has been associated with allergic reactions with FIX replacement therapies, including with rFIXFc. Subjects experiencing allergic reactions should be evaluated for the presence of an inhibitor.

Subjects (as appropriate) and parents/legal guardians of subjects will be informed of the early symptoms and signs of thrombotic phenomena, including pain and/or tenderness along a vein, unexpected swelling of an arm or leg without pain or tenderness, redness along a vein, low fever without any known reason (such as a cold or flu), sudden shortness of breath or difficulty breathing, or coughing, sudden chest pain, sudden severe headache or changes in vision, and numbness or tingling in arms or legs. If such an event occurs while the subject is at home, the parents/legal guardians will be instructed to seek immediate medical care for the subject.

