#### **9.4.3.1. Endpoint Definition**

A positive inhibitor occurs where a patient has a value  $\geq 0.6$  Bethesda Units (BU/mL) confirmed on re-testing 2-4 weeks later. See Section 5.2.4 for exact definition. Results from blood samples collected during surgical/rehabilitation periods for the purpose of determining the presence of an inhibitor will be included in this analysis. Inhibitor test data will be listed for all patients.

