#### **9.4.3.2. Primary Analysis**

The primary analysis of overall incidence of positive inhibitor formation will be based on all patients in the Safety Analysis Set. Any patient who develops an inhibitor following the initial rFIXFc administration will be included in the numerator. All patients who have received at least 1 dose of rFIXFc will be included in the denominator. An exact 95% confidence interval for the proportion of patients with a positive inhibitor will be calculated using the Clopper-Pearson method for a binomial proportion. PROC FREQ in SAS version 9.4 or higher will be used to produce this confidence interval.

The incidence of positive inhibitor formation will be summarized separately for the types of inhibitor specified in Section 5.2.4, namely:

- Patients with high-titer inhibitors
- Patients with low-titer inhibitors that meet the clinically meaningful criteria
- Patients with low-titer inhibitors that do not meet the clinically meaningful criteria

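### The 2-to-4-week confirmation window is part of the primary endpoint, and nothing says how to classify an inhibitor result confirmed late or never retested

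*SAP*

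**What the plan says.** - **Definition.** SAP 5.2.4 requires two central-laboratory results of at least 0.60 BU/mL, the second "from a separate sample, drawn 2 to 4 weeks following the original sample". Protocol 10.2.4 uses the same window: "drawn 2 to 4 weeks following the original sample. Both tests must be performed by the central laboratory".
- **Endpoint.** SAP 9.4.3.1 takes this over unchanged: "confirmed on re-testing 2-4 weeks later. See Section 5.2.4 for exact definition".
- **Primary proportion.** SAP 9.4.3.2 states: "Any patient who develops an inhibitor following the initial rFIXFc administration will be included in the numerator". The denominator is everyone with at least one dose. No evaluable or confirmatory test is needed to be in it.
- **Missing data.** SAP 5.5 allows imputation only for listed exceptions, and none concerns inhibitor tests.
- **Safeguards.** Protocol 10.2.4 requires a valid inhibitor result from the ET/EOS Visit and foresees an extra visit to confirm a positive. Protocol 15.3.2 says that subjects with allergic reactions should be evaluated for an inhibitor. SAP 9.4.3.1 lists all inhibitor results.
- **What is absent.** SAP 5.2.4 settles discordant titres by two results out of three. It has no rule for a second positive drawn outside the window, or for a first positive that is never retested.

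**The concern.** A collection window tells sites when to draw a sample. Here it also decides who is an event. A subject whose second positive came a week late, or who left before a second draw, falls out of the numerator but stays in the denominator.

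The loss need not be random. Protocol 11 requires withdrawal for "Development of a Grade 2 or greater allergic drug reaction in association with the administration of rFIXFc", and protocol 15.3.2 says of allergic reactions: "These events often occur in close temporal relation with the development of FIX inhibitors". Subjects with an inhibitor may therefore be over-represented among those who leave before a timely second sample.

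The SAP is more cautious with ordinary adverse events. A missing severity is counted as severe (9.3.5) and a missing relationship as related (9.3.6). A missing confirmation on the study's only primary endpoint has no rule and, by construction, defaults to no event.

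**Working it through.** The plan gives no expected inhibitor rate or target precision, and the sample size of about 30 is set on clinical grounds. There is therefore no planned figure to reproduce.

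**1. How the literal rule classifies each case**

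| First result at least 0.60 BU/mL, then | Meets SAP 5.2.4 | Numerator | Denominator |
|---|---|---|---|
| second at least 0.60, at 3 weeks | yes | 1 | 1 |
| second at least 0.60, at 5 weeks | no | 0 | 1 |
| second at least 0.60, at next interim visit | no | 0 | 1 |
| no later evaluable sample | no | 0 | 1 |
| second below 0.60, at 3 weeks | no | 0 | 1 |

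Only the last row is a positive that a retest contradicted. The primary proportion cannot tell it from the three rows above it.

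**2. Whether planned visits supply the second sample**

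Interim visits are every 12 (±2) weeks, so consecutive visits are 12 − 4 = 8 to 12 + 4 = 16 weeks apart. That is never within 2 to 4 weeks.

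Exposure-day milestones are at 3–7, 10–15, 20–25 and 50–55 EDs. If doses are weekly and no others are given (an assumption), the shortest gaps are:
- first to second: 10 − 7 = 3 weeks, which can fall in the window
- second to third: 20 − 15 = 5 weeks
- third to fourth: 50 − 25 = 25 weeks

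Extra doses for bleeding shorten these gaps, and a milestone visit may happen to fall near an interim visit. Otherwise an added visit is needed.

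**3. Timing after withdrawal for an allergic reaction**

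Assume the first sample is drawn right after the 72-hour washout, at about day 3 from the last dose. The confirmation window is then day 3 + 14 = 17 to day 3 + 28 = 31. The final safety contact "will be conducted 14 (+7) days after the last dose of rFIXFc", which is days 14 to 21, and it may be a telephone call. Most of the window follows the last planned contact, so the draw depends on a specially arranged visit.

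**4. Size at n = 30**

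The method is the SAP's own, Clopper-Pearson. The lower limit is the 2.5% quantile of Beta(x, n − x + 1), and the upper limit is the 97.5% quantile of Beta(x + 1, n − x). For x = 0 the upper limit is 1 − 0.025^(1/30) = 11.6%.

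| Events | Proportion | 95% CI |
|---|---|---|
| 0/30 | 0% | 0 to 11.6 |
| 1/30 | 3.3% | 0.1 to 17.2 |
| 2/30 | 6.7% | 0.8 to 22.1 |
| 3/30 | 10.0% | 2.1 to 26.5 |

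Each reclassified subject moves the estimate by 1/30 = 3.3 percentage points.

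**5. How likely at least one such case is**

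This rests on assumed inputs only. Let p be the true inhibitor rate and m the share of true cases without an in-window confirmation. The chance that at least one of 30 subjects is affected is 1 − (1 − pm)^30.

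| p | m = 10% | m = 50% |
|---|---|---|
| 2% | 6% | 26% |
| 5% | 14% | 53% |
| 10% | 26% | 79% |

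**6. Other analyses**

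In the ED-milestone analysis (SAP 9.4.3.3), an unconfirmed subject who stops before the milestone leaves the denominator as well. In the Kaplan-Meier analysis he is censored at his last ED. The effect in step 4 belongs to the primary proportion.

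**The case against.** The strongest reply is that the protocol already makes the problem unlikely. A second sample is part of the definition, so confirmation is not optional; what is conditional is the extra visit, because the draw may fall at a visit already planned. Withdrawn subjects have ET/EOS assessments with a required valid inhibitor result. SAE reporting, DSMC review and ITI eligibility all depend on inhibitor results, so leaving a first positive unconfirmed for 8 to 16 weeks would be a failure of conduct. All inhibitor results are listed, with a separate listing of abnormal ones (SAP Section 12), so in about 30 subjects every such case can be seen. No hypothesis is tested, and the intervals in the table overlap heavily.

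Most of this stands, and it rules out three stronger readings that a reader might infer:

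- **That the primary endpoint is biased downward.** The documents give no frequency of late or missed confirmation. If there are no such cases, there is no bias.
- **That inhibitor sampling stops at the 14 (+7)-day contact.** Protocol 7.3.3 describes that contact as a check on adverse events and concomitant treatments and procedures. Nothing in protocol 10.2.4 makes it a cut-off for confirmatory draws.
- **That two positives 5 weeks apart can never become an event.** The second could serve as a new first sample, confirmed 2 to 4 weeks later. The SAP neither allows nor forbids this.

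What the reply does not do is supply a classification. An ET/EOS test, an unscheduled visit and a listing all leave the numerator in 9.4.3.2 unchanged when the second sample is late or absent.

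**Conclusion.** The point holds as a gap in the endpoint rule. The 2-to-4-week window is part of the definition, the denominator is all dosed subjects, and no text classifies a late or absent confirmation. Read literally, such subjects count as inhibitor-free. Undercounting is a risk, and it may be informative because of the allergic-withdrawal route, but it is not a demonstrated bias.

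One affected subject at n = 30 is worth 3.3 percentage points, and moves the upper limit by 5.6 points (17.2 − 11.6) from zero events or 4.9 points (22.1 − 17.2) from one. This assumes about 30 dosed subjects and zero to two affected. It should be settled before the final analysis, as a cheap improvement.

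**What to change.** 1. In SAP 5.2.4 and 9.4.3.1, state that for analysis a second, separate central-laboratory result of at least 0.60 BU/mL drawn more than 4 weeks after the first, with no intervening negative, counts as confirmation. Report the late draw as a protocol deviation. Keep the existing rule that dates the inhibitor from the first positive later confirmed.
2. Add one sensitivity row to the inhibitor table that also counts as events subjects with a post-exposure central-laboratory result of at least 0.60 BU/mL and no later evaluable sample. This row also picks up a subject whose second positive was drawn before 2 weeks and who was not sampled again.
3. List the difference from protocol 10.2.4 in SAP Section 10, which at present names no change to the inhibitor definition. Leave the protocol's definition as it is for SAE reporting, withdrawal and ITI eligibility.

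The cost is SAP wording, a Section 10 entry and one table row, with no change to visits or treatment. The reported rate may be slightly less favourable. The sensitivity row gives up some of the specificity that confirmation provides, which is why it should not replace the primary analysis.

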**5.2.5. Subgroup Definitions**

**Surgery Subgroup**

The Surgery Subgroup is defined as all patients who have undergone major surgery after first dose of study drug. This set will be described in the disposition table and all analyses and listings of major surgeries will be presented for this population.

	Statistical Analysis Plan	Final v1.0
---	----------------------------------	-------------------

